Food and nutrition related problems represent a major cause of excess morbidity and mortality in many emergency-affected populations. Nutritional status frequently deteriorates because emergency-affected populations are often displaced from their usual sources of food and income. Moreover, many displaced populations are composed largely of subsistence farmers who are removed from their land and who have little or no alternate sources of income with which to purchase food. Wage earners in displaced populations lose their source of income with which to purchase food. In addition to these factors which lead to a deficit in families' ability to procure food, warring factions will often directly interfere with food production and distribution in order to adversely affect specific populations. Even in the absence of population displacement, civil conflict often disrupts the normal mechanisms of food production and distribution, leading to a decline in access to food among part or all the affected population.

In addition to factors determining the available supply of food, an increase in the incidence of communicable diseases often leads to deterioration in nutritional status. Communicable diseases are generally more common in emergency-affected populations because disease prevention programs, such as immunization, are disrupted by conflict, economic chaos, and general social disruption. Moreover, population displacement often leads to settlement in camps with high population densities, poor sanitation, few health services, and other factors facilitating the spread of communicable diseases.

The peak disruption and subsequent population displacement are frequently preceded by a period of gradual social breakdown. Health, education, economic, and other activities are

partially or completely disrupted. The final population displacement is often an indicator of chronic disruption which has finally become severe enough to threaten survival. As a result of all these factors, many affected populations suffer from both protein-energy malnutrition and micronutrient deficiencies.

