Nutrition assessment surveys are most commonly cross-sectional descriptive surveys used to estimate the prevalence rates of various types of malnutrition. Surveys can also assess the role of risk factors and identify vulnerable subgroups. Surveys will often be carried out in many different situations and populations, such as 1) in refugee camps or camps for internally-displaced persons which are organized and run by local government authorities or international organizations; 2) in displaced populations which are integrated into a local host population; and 3) in emergency-affected populations which are not displaced. Surveys in non-displaced populations are similar to those done in stable populations not affected by emergencies.

Objectives

The objectives of nutrition assessment surveys in emergency-affected populations usually include at least some of the following:

- 1) Estimate the current prevalence of acute malnutrition (wasting) and chronic malnutrition (stunting) among children 6-59 months of age.
- 2) Estimate the current prevalence of protein-energy malnutrition among women of childbearing age (15-49 years of age).
- 3) Estimate the current prevalence and severity of anemia among children 6-59 months of age, women of child-bearing age, and possibly adult men age.
- 4) Estimate the current prevalence and severity of vitamin A deficiency among children 6-59 months of age and women of child-bearing age.
- 5) Estimate the current prevalence and severity of other micronutrient deficiencies in various target population groups. Such deficiencies and target groups may include iodine deficiency in children 8-11 years of age; B vitamin deficiency in children, adolescents, or adults; vitamin D deficiency in children 6-59 months of age; or others.
- 6) Estimate current household food consumption patterns, household food security, and food consumption in children 6-59 months of age.
- 7) Estimate the measles immunization coverage among children 9-59 months of age.
- 8) Estimate the cumulative 2-week prevalence of diarrheal disease and acute lower respiratory infection in children 6-59 months of age.
- 9) Estimate the crude mortality rate and age-specific mortality rate for children less than 5 years of age.

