BMI MUAC	Normal (BMI > 18.5)	At risk (17.0 > BMI<18.4)	Moderate (16.0 > BMI<17.0)	Severe (16.0 <bmi)< th=""></bmi)<>
Normal	Normal	Normal?	Mild (Category I)	Moderate (Category II)
Low	Normal?	Mild (Category I)	Moderate (Category II)	Severe (Category III)

Because BMI is not valid in pregnant women, MUAC measurements are sometimes used in this group to assess protein-energy malnutrition. Although no international consensus exists, malnutrition in pregnant women is often defined as a MUAC less than 22.0 cm.

Anemia: The cut-off points for hemoglobin concentration used to define anemia depend on the age and sex-group of the person tested, as shown below.

Age or sex group	Hemoglobin concentration (g/dL) defining anemia
Children 6 months - 5 years	< 11.0
Children 5-11 years	< 11.5
Children 12-13 years	< 12.0
Non-pregnant girls and women >13 years	< 12.0
Pregnant women > 13 years	< 11.0
Boys and men >13 years	< 13.0

Hemoglobin concentrations must be adjusted for survey subjects who live at high altitude. The adjustment is shown below.

Altitude range	Increase in cut-off
(in meters)	point defining anemia(g/dL)
alt < 1000	No adjustment
1000< alt <1250	+0.2
1250< alt <1750	+0.5
1750< alt <2250	+0.8
2250< alt <2750	+1.3
2750< alt <3250	+1.9
3250< alt <3750	+2.7
3750< alt <4250	+3.5
4250< alt <4750	+4.5
4750< alt <5250	+5.5
5250< alt	+6.7

In some surveys in which measurement of hemoglobin concentration will not be possible, survey subjects are examined for the presence of pallor, indicating moderate and severe anemia. Pallor is most often sought on the palms, but may also be examined in the conjunctiva, buccal mucosa, and nail beds.

Vitamin A: A serum retinol concentration less than 0.35 : mol/l (10 I.U.) defines deficiency. Serum retinol levels of 0.35 - 0.69 : mol/l (10-19 I.U.) indicate low retinol levels. In surveys where obtaining the appropriate biologic specimen for measurement of serum retinol is not feasible, survey subjects may be examined for the presence of Bitot's spots or questioned about the presence of night blindness. Night blindness is often difficult for a mother to detect in children less than 24 months of age.

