Survey teams will record for each selected household or individual in the survey sample the following information, 1) whether consent was given, 2) whether data collection was completed, and, 3) if data were not collected, why. These data will allow calculation of response rates and the determination of reasons for nonresponse.

Consent process

Prior to enrollment, verbal consent will be obtained from adults and parents or caretakers of children selected for participation in the survey. For further information on consent procedures, see the section below "Supplemental information for protection of human research participants."

Variables/interventions

Variables

Below are listed some of the variables which may be collected in a nutrition assessment survey in an emergency-affected population

- I. Household data
 - A. Number of family members
 - B. Household income
 - C. Amount of money spent on food per month
 - D. Duration of residence in this location
 - E. Source of water: (central system, truck, reservoir, well, surface water, other)
 - F. Receipt of relief food
 - G. Household food stores available
 - H. Household food security
 - I. Iodine testing of household salt

- II. Individual household members
 - A. Age
 - B. Sex
 - C. Status now (Alive in household, alive elsewhere, dead, unknown)
- III. Children 6-59 months of age currently in household
 - A. Date of birth or age in months
 - B. Sex
 - C. Vaccination status
 - 1. BCG by scar and by mother's history and/or vaccination card
 - 2. OPV
 - 3. DPT
 - 4. Measles
 - D. Nutritional status
 - 1. Food consumption history: (24 hour recall)
 - 2. Acute protein-energy malnutrition
 - a. Weight
 - b. Height
 - c. Mid-upper arm circumference: (MUAC)
 - d. Edema
 - 3. Anemia
 - a. Hemoglobin
 - b. Transferrin receptor concentration
 - c. Serum C-reactive protein concentration
 - d. Serum folate concentration
 - 4. Vitamin A
 - a. Presence of night blindness
 - b. Presence of Bitots spots
 - c. Serum vitamin A level
 - 5. Vitamin C
 - a. Symptoms
 - b. Examination of gums and joints
 - 6. Vitamin D
 - a. Symptoms
- IV. Children 8-11 years of age
 - A. Date of birth
 - B. Examination for goiter
 - C. Urinary iodine
- V. Women of child-bearing age currently in household
 - A. Age
 - B. Education level
 - C. Pregnancy status
 - D. Weight
 - E. Height
 - F. MUAC
 - G. Examination for goiter

H. Hemoglobin

- VI. Adult men: (>18 years of age) currently in household
 - A. Hemoglobin: (subsample)

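### Serum retinol is classified by fixed cut-offs regardless of infection, so the share with low retinol can be overstated; C-reactive protein, an optional variable for the same children, is given no role in reading it

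*Protocol*

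**What the plan says.** One objective is to "Estimate the current prevalence and severity of vitamin A deficiency among children 6-59 months of age and women of child-bearing age" (Protocol, Objectives, item 4). The case definition that serves it has two fixed steps. "A serum retinol concentration less than 0.35" µmol/l defines deficiency, and "Serum retinol levels of 0.35 - 0.69 : mol/l (10-19 I.U.) indicate low retinol levels" (the colon stands for a micro sign lost in conversion). No condition for infection or inflammation is attached. By contrast, the same section requires the hemoglobin cut-off to be shifted for altitude.

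On infection, Justification for survey states: "Communicable diseases are generally more common in emergency-affected populations". Objective 8 and the case definitions also cover diarrhea and acute lower respiratory infection in the prior two weeks.

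The variable list opens "Below are listed some of the variables which may be collected in a nutrition assessment survey", so it is a menu. For children 6-59 months it has "Serum C-reactive protein concentration" under Anemia and "Serum vitamin A level" under Vitamin A. For women it has neither, although the specimen table under Data collection gives adult women as a common target group for vitamin A. No section states a use for C-reactive protein. The sections on analysis, bias and limitations do not connect infection with retinol.

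**The concern.** If circulating retinol drops for a time during the acute-phase response, a child with a current infection can fall below a cut-off while having adequate vitamin A stores. A prevalence built on raw values then mixes vitamin A status with current infection, in populations where the Protocol itself expects infection to be frequent.

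Two uses are exposed:

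- **The level.** The Protocol says that the type, extent and urgency of interventions depend on survey findings.
- **Comparisons.** Subgroups are compared by chi-square, and later surveys serve to evaluate programs. Groups or rounds with different infection levels could differ in low retinol with no difference in vitamin A status.

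A larger sample does not reduce this kind of error, and training and supervision do not remove a biological effect on a correctly measured value.

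**Working it through.** **No plan figure to reproduce.** The Protocol gives no vitamin A prevalence, and its sample-size table has no vitamin A row. What follows is an illustration.

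**Inputs from the Protocol:** cut-offs c = 0.35 and c = 0.70 µmol/l (the upper end of the low band, 0.69, taken as below 0.70).

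**Inputs assumed, none of them in the Protocol:**
- retinol is lognormal with log SD s = 0.35;
- median without inflammation m = 0.9 or 1.0 µmol/l;
- share of children inflamed f = 0.2 to 0.4;
- proportional fall in retinol while inflamed r = 0.1 to 0.3.

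**Formula.** Observed share below c = (1 − f) × Φ[ln(c/m)/s] + f × Φ[ln(c/(m(1 − r)))/s]. The true share is the first Φ term alone, so the overstatement is f times the difference between the two Φ terms.

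**Worked case:** c = 0.70, m = 0.9.
- True: ln(0.70/0.9)/0.35 = −0.718, Φ = 0.236.
- Mild corner, r = 0.1, f = 0.2: ln(0.70/0.81)/0.35 = −0.417, Φ = 0.338. Observed = 0.8 × 0.236 + 0.2 × 0.338 = 0.257.
- Strong corner, r = 0.3, f = 0.4: ln(0.70/0.63)/0.35 = 0.301, Φ = 0.618. Observed = 0.6 × 0.236 + 0.4 × 0.618 = 0.389.

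**Results**

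| Cut-off (µmol/l) | Median (µmol/l) | True share | Observed, mild to strong | Shift, points |
|---|---|---|---|---|
| 0.70 | 0.9 | 23.6% | 25.7-38.9% | 2.0 to 15.3 |
| 0.70 | 1.0 | 15.4% | 17.1-29.2% | 1.6 to 13.8 |
| 0.35 | 0.9 | 0.35% | 0.44-2.07% | 0.1 to 1.7 |
| 0.35 | 1.0 | 0.14% | 0.18-1.03% | 0.04 to 0.9 |

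**A comparison with unchanged vitamin A status.** With c = 0.70, m = 0.9 and r = 0.2, the inflamed term is Φ[ln(0.70/0.72)/0.35] = Φ(−0.080) = 0.468. At f = 0.2 the observed share is 0.8 × 0.236 + 0.2 × 0.468 = 28.3%. At f = 0.4 it is 0.6 × 0.236 + 0.4 × 0.468 = 32.9%. Two rounds would differ by 4.6 points from infection alone.

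**Sensitivity to the assumptions.** A second set fixes the true share below 0.70 at 20%, with log SD 0.3-0.4.
- f = 0.2, r = 0.1: 21.6-22.2% observed.
- f = 0.4, r = 0.2: 27.5-30.4% observed.
- f = 0.6, r = 0.3: 39.2-46.1% observed. Here the share below 0.35 goes from 0.1-0.5% to 1.5-3.0%.

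At r = 0 there is no bias; for any r > 0 it is upward.

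**For scale.** The Protocol's wasting example asks for a precision of 5 points at 20% prevalence. The upper part of the range for the 0.70 cut-off exceeds that margin; the lower part does not.

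**The case against.** The strongest reply is that this is silence in a generic document, not a wrong statement. The analysis section says it cannot list every analysis and uses hemoglobin only as an illustration. An inflammation adjustment could sit in a survey-specific analysis plan, and fixed cut-offs do not forbid one. That is fair as far as it goes: the Protocol cannot be said to have decided to ignore infection. But the case definition is stated without condition, and following it as written gives the raw classification.

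Three stronger readings are tempting, and the document does not support them.

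- **That deficiency is overstated.** The Protocol never says that infection lowers retinol. The premise is general subject knowledge and every size is assumed, so only a risk can be claimed.
- **That deficiency is off by 2 to 15 points.** That range is for all values below 0.70 µmol/l. The Protocol calls only values below 0.35 deficient, and there the shift is small under the same inputs.
- **That the conclusion should rest on a corrected figure alone.** Objective 4 concerns all children 6-59 months. Restricting to those with normal C-reactive protein changes that target and, if infected children are truly more deficient, biases prevalence downward.

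The limits on the link between the two markers also stand. Both are optional, they sit under different headings, and nothing says that one survey will measure both. Neither is listed for women.

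**Conclusion.** The concern holds as a risk that the Protocol leaves open. It fixes retinol cut-offs without regard to infection, expects more infection in its populations, and lists C-reactive protein for the same children without a use for retinol. If retinol falls during the acute-phase response, the share below 0.70 µmol/l can be overstated by roughly 2 to 15 points, and the share below 0.35 µmol/l by less than about 2 points. Both sizes assume 20-40% of children inflamed, a 10-30% fall, medians of 0.9-1.0 µmol/l and log SD 0.35; heavier infection would enlarge them. The upward direction needs only that some fall occurs. The size cannot be settled from the Protocol. Comparisons across subgroups or rounds are affected when infection levels differ between them.

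**What to change.** Add to the Vitamin A case definition or the analysis plan:

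1. In surveys that measure both retinol and C-reactive protein, report low and deficient retinol unadjusted for all children, and also adjusted for C-reactive protein. Prefer a regression correction, which keeps every child.
2. Give results by C-reactive protein status as a sensitivity analysis.
3. Interpret the vitamin A conclusion in light of both figures, including comparisons between subgroups or rounds.
4. Where C-reactive protein is not measured, including in women, name infection as a limitation of the retinol prevalence.

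The cost is a little analysis work, with no new specimen where C-reactive protein is already measured. The adjusted figure relies on a correction model: it can over-correct if deficient children are also more often infected, which is why the unadjusted figure stays beside it. Any subset with normal C-reactive protein will have wider intervals.

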	Per son no.	Age (years)	Sex (circle one)	Curren as of T (circl	nt Status TODAY le one)	If missing or dead, since when? (mm/yy)	Died of which cause? (ask questions)	Walnutrition?	Pregnant or in Chel??
\vdash	1		M / F	1 2	3 4	/		Y / N	Y / N
	2		M / F	1 2	3 4	/		Y / N	Y / N
	3		M / F	1 2	3 4	/		Y / N	Y / N
	4		M / F	1 2	3 4	/		Y / N	Y / N
	5		M / F	1 2	3 4	/		Y / N	Y / N
	6		M / F	1 2	3 4	/		Y / N	Y / N
	7		M / F	1 2	3 4	/		Y / N	Y / N
	8		M / F	1 2	3 4	/		Y / N	Y / N
	9		M / F	1 2	3 4	/		Y / N	Y / N
	10		M / F	1 2	3 4	/		Y / N	Y / N
	11		M / F	1 2	3 4	/		Y / N	Y / N
	12		M / F	1 2	3 4	/		Y / N	Y / N
	13		M / F	1 2	3 4	/		Y / N	Y / N
	14		M / F	1 2	3 4	/		Y / N	Y / N
	15		M / F	1 2	3 4	/		Y / N	Y / N

LIVING WOMEN OF CHILDBEARING AGE (15 – 49 years)

Person no. from table 1 above.	Literate ?	Night blind- ness	Goiter	Preg- nant now?	No. of doses tetanus vaccine	MUAC (cms)	Weight (kgs)	Height (cms)	Hemoglobin (gms)
	Y/N	Y / N	Y / N	Y / N				,,,	
	Y/N	Y / N	Y / N	Y / N				,,	, ,
	Y/N	Y / N	Y / N	Y / N		,	,	,,	, ,
	Y/N	Y / N	Y / N	Y / N		,,	,	,,	,,
	Y/N	Y / N	Y / N	Y / N		,,	,	,,	,,
	Y/N	Y / N	Y / N	Y / N		,	,	,,	,,
	Y/N	Y / N	Y / N	Y / N		,	,	,,	,,
	Y/N	Y / N	Y / N	Y / N		,	,	,,	,,
	Y/N	Y / N	Y / N	Y / N		,	,	,	,
	Y/N	Y / N	Y / N	Y / N					

Clus	ster number:	HH:	_ Child's person number:	Mot	ner's pers	son number:				
Que	stions for adult ca	retaker								
1) F	Relationship of res	pondent to ch	ild:	. Mother	Father	Grandmothe	er Grand	dfathe	r O	ther
2) I	s this child's mothe	er alive?					.Yes	/ N o	/	Unk
3) 5	Sex						M a	le /	Fer	nale
4) [Date of birth OR Ag	ge in months.			/	/	OR _		mo	nths
				[Day Mo	onth Year.				
5) [Does this child hav	e difficulty see	eing at night or in the evenin	g when ot	her peop	ole do not?	Yes	N o	/	Unk
6) 5	Since this time yes	terday, has th	is child breast fed?				Yes /	N o	/	Unk
	6a) If YES, was	breast milk th	is child's main source of foo	d since ye	sterday?		Yes ,	/ N o	/	U nk
	6b) If YES, how	long after birt	h did this child first breastfee	ed?			······		_ h	ours
7) \$	Since this time yes (circle all that are)	terday, has th true) P	is child received anything ot owered milk or infant formul	her than b a / S emi-	reast mil solid or s	lk? solid food / No	Water, one of t	tea, c hese	or ju	ice /
8) \$	Since this time yes	teday, has thi	s child drunk anything from a	a bottle wi	th a nipp	le?	.Yes	/ N o	/	Unk

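### Night blindness is asked from 6 months of age with no age limit, denominator or rule for unknown answers, although the protocol itself doubts its detection below 24 months

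*Protocol*

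**What the plan says.** - **Case definitions, Vitamin A.** Deficiency is defined by serum retinol. Where a suitable specimen cannot be obtained, "survey subjects may be examined for the presence of Bitot's spots or questioned about the presence of night blindness". The next sentence is the caution: "Night blindness is often difficult for a mother to detect in children less than 24 months of age". No age limit, separate reporting or denominator follows from it.
- **Objectives, item 4.** "Estimate the current prevalence and severity of vitamin A deficiency among children 6-59 months of age and women of child-bearing age".
- **Variables, part III.** Under the heading "Children 6-59 months of age currently in household" stands the item "Presence of night blindness", without restriction. The list is illustrative; it gives "some of the variables which may be collected in a nutrition assessment survey".
- **Appendix 1, child form, question 5.** The adult caretaker is asked whether the child has trouble seeing in the evening or at night. The answers are Yes, No or Unk, and there is no age skip. Age is recorded in question 4, as date of birth or in months.
- **Data analysis plan.** Prevalence is obtained by calculating proportions. Hemoglobin is the only outcome worked through, and the section says that not every analysis can be fixed in advance. Nothing is said about night blindness or Unk answers.

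**The concern.** The protocol identifies an age band in which its substitute indicator works poorly, then collects the indicator across that band without saying how the band is to be analysed. An analyst who follows the text as it stands would most naturally divide positive answers by all children 6-59 months. Children under 24 months would then add to the denominator with a reduced chance of adding to the numerator.

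The resulting prevalence would be too low. The shortfall would also move with the share of young children and with how teams code a mother who cannot tell, so surveys would not be comparable. The section on collection of biologic specimens already accepts that clinical signs understate micronutrient deficiency; this would be a second and avoidable understatement. It matters in surveys without retinol, because the protocol says that the type, extent and urgency of interventions depend on the findings. The section on bias does not mention the problem.

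Elsewhere the protocol does fit the age range to the indicator: 9-59 months for measles coverage and 8-11 years for iodine.

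**Working it through.** The protocol gives no night-blindness prevalence, sample size or bias, so there is no figure of its own to reproduce.

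**Inputs from the protocol:** age range 6-59 months; detection threshold 24 months; answers Yes/No/Unk. The sample size table gives n = 492 and design effect 2 for wasting in children 6-59 months; these are borrowed below only to illustrate precision, since the table has no vitamin A row.

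**Assumptions, not in the protocol:**
- w, the share of children under 24 months. Uniform ages over 54 one-month bands give 18/54 = 33.3%; range 30% to 40%.
- s, detection below 24 months relative to older children; range 0 to 1.
- r, true prevalence below 24 months divided by that at 24-59 months; base case 1, range 0.5 to 1.5.
- u, the fraction of under-24-month children coded Unk and dropped; base case 0.

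**Step 1. All children 6-59 months in the denominator, missed cases coded No.**

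Relative loss = 1 − [w·r·s + (1 − w)] / [w·r + (1 − w)]. With r = 1 this reduces to w(1 − s).

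| w | r | s | Relative loss |
|---|---|---|---|
| 1/3 | 1 | 0 | 33.3% |
| 1/3 | 1 | 0.25 | 25.0% |
| 1/3 | 1 | 0.50 | 16.7% |
| 1/3 | 1 | 0.75 | 8.3% |
| 1/3 | 1 | 1 | 0% |
| 0.30 | 1 | 0 | 30.0% |
| 0.40 | 1 | 0 | 40.0% |
| 1/3 | 0.5 | 0 | 20.0% |
| 1/3 | 1.5 | 0 | 42.9% |

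For illustration, at a 33.3% loss an assumed true 1.5% would be reported as 1.5 × 36/54 = 1.0%.

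**Step 2. Some young children coded Unk and dropped, the rest coded No (w = 1/3, r = 1).**

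Relative loss = 1 − (1 − w) / [(1 − w) + w(1 − u)].

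- u = 0: 33.3%
- u = 0.25: 27.3%
- u = 0.50: 1 − 0.667/0.833 = 20.0%
- u = 0.75: 11.1%
- u = 1: 0%

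**Step 3. Precision after restriction to 24-59 months.**

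With uniform ages, 492 × 36/54 = 328 children remain. Half-width = 1.96 × √(2 × p(1 − p)/n), at an assumed p = 1.5%:

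- n = 492: 1.96 × √(2 × 0.015 × 0.985/492) = 1.5 points
- n = 328: 1.96 × √(2 × 0.015 × 0.985/328) = 1.9 points
- ratio: √(492/328) = 1.22, so about 22% wider

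**The case against.** The strongest reply is that collecting an answer biases nothing. Age is on the form, so an analyst can restrict to 24-59 months at any time, and a separate analysis plan may already say so. The caution in the case definition can be read as exactly that warning. The variable list and the form are examples. Night blindness is optional, and Bitot's spots are the alternative sign, recorded on the same form. A mother who cannot tell may answer Unk. The protocol states no night-blindness threshold for action, and where it names a sign as a reason to give vitamin A, the sign is Bitot's spots. Finally, the illustrative shift from 1.5% to 1.0% is smaller than the 1.5-point half-width of a single survey.

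Much of this stands. A reader might infer that the protocol counts all children 6-59 months in the night-blindness denominator. It does not say so; that is only the natural default. A reader might also take one third as the upper limit of the loss. It is not: it rises to 40% with a younger sample and 43% if true prevalence is 1.5 times higher below 24 months. It is not the expected value either, because often difficult does not mean impossible.

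What does not stand is that the matter can therefore be left alone. The eligible age of an indicator belongs to its case definition, which this protocol chose to write. It names the age problem there and gives no rule. Sampling error in one survey also does not excuse a downward bias that would recur in every survey using the default.

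**Conclusion.** The point holds in a conditional form. The protocol lists and asks night blindness from 6 months without an age limit, despite its own caution below 24 months, and fixes neither a denominator nor the treatment of Unk. Prevalence is understated if the 6-59 month group is used as the denominator and missed cases are coded No.

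With uniform ages and equal true prevalence, the relative loss runs from 8% at 75% detection below 24 months, through 17% at half detection, to 33% at none. It could be larger in a younger sample, and it shrinks to nothing if every child under 24 months is coded Unk and dropped. The age mix, detection and coding are all assumptions, so no single figure should be quoted as the bias. The point reaches only surveys that use this optional indicator. It is a cheap improvement, not a demonstrated error in any reported estimate.

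**What to change.** In the Vitamin A case definition, add that the night-blindness indicator in children is defined for ages 24-59 months, in both numerator and denominator. Report ages 6-23 months separately or not at all. Report the number of Unk answers and exclude them from the denominator. The question may still be asked of all children, and no new data are needed.

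The cost is one line of text and some precision: about one third fewer children with uniform ages, and a 95% interval about 22% wider if the design effect and prevalence are unchanged.
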